3.2. Secondary endpoints

- Comparison of time from end of treatment to recurrence on condition that the patient is in complete remission at the end of treatment between patients treated with maintenance therapy vs. patients without maintenance therapy.
- Cytokine response in serum and tissue
- Quality of life
- HADS

4. Patient selection criteria

4.1. Inclusion Criteria:

- Histopathologically documented MF clinical stage IA-IIB (see Table1) confirmed by current or previous diagnostic lesion biopsy
- A Karnofsky performance score ≥ 60 (see Table 2)
- Age ≥ 18 years - ≤ 85
- Anti-ds-DNA (antinuclear antibodies) AND anti-Ro/La antibodies: negative
- Acceptable organ function defined as follows:

SGOT (AST) and SGPT (ALT) ≤ 2.5 times the upper limit of normal for the institution

- Creatinine ≤ 2 times the upper limit of normal for the institution
- No evidence of severe cardiac insufficiency (NYHA grade III-IV)
- Women of child bearing potential must have a negative serum or urine pregnancy test (β -HCG) within seven (7) days prior to randomization
- Absence of any serious intercurrent illness or infection at time of entry into the study that could interfere with planned treatment
- Patients must be willing to accept limiting sun exposure on the day receiving PUVA treatment
- Written informed consent

4.2. Exclusion criteria:

- Pregnancy and Lactation
- Photosensitive diseases such as lupus erythematosus or basal cell nevus syndrome
- Skin cancer syndromes such as Xeroderma pigmentosum or basal cell nevus syndrome
- PUVA (oral or topical) treatment within the last 3 months

5. PUVA treatment and follow-up

Psoralens are photosensitising agents. Methoxsalen – the most commonly used drug is a psoralen derivative that is structurally and pharmacologically related to trioxsalen. For PUVA treatment 8-methoxypsoralen (8-MOP) will be used. Patients receive a liquid preparation of 8-MOP (10 mg) in soft gelatine capsules (Oxsoralen®; Gerot Pharmazeutika GmbH, Vienna, Austria, please refer to the Summary of Product Characteristics). The dose of 8-MOP is based on the patient's weight. The standard dose of approximately 10 mg per 20 kg body weight will be given 1 h before UVA exposure, according to the following table:

| Body weight (kg) | 8-MOP (Oxsoralen) dose (10mg = 1 Cps) mg = Cps |
|-------------------------|---|
| < 30 | 10 = 1 |
| 30 - 50 | 20 = 2 |
| 51 - 65 | 30 = 3 |
| 66 - 80 | 40 = 4 |
| 81 - 90 | 50 = 5 |
| 91 - 115 | 60 = 6 |
| > 115 | 70 = 7 |

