| mild (+) | loss of appetite without alteration in eating habits |
| moderate (++) | oral intake decreased without significant weight loss, dehydration or malnutrition |
| severe (+++) | inadequate oral caloric or fluid intake |

Vomiting:

| | |
|---------------|--------------------------|
| none (-) | |
| mild (+) | 1 episode in 24 hours |
| moderate (++) | 2-5 episodes in 24 hours |
| severe (+++) | ≥ 6 episodes in 24 hours |

After 12 weeks of treatment or thereafter at week 16, 20 or 24 (after 24, 32, 40, or 48 PUVA treatments, respectively) patients with complete remission will be randomized by a computer generated list for treatment allocation into two arms (arm A and B, see below). Patients who haven't experienced complete remission after 24 weeks will discontinue active study participation and will enter an observatory study arm.

Patients with complete response will be randomized to receive either PUVA-maintenance therapy (arm A) or no maintenance therapy (arm B) (Figure 1)

Arm A: oral 8-MOP+UVA

Patients will be treated with PUVA maintenance therapy at constant single UVA doses (UVA-dose will be the same as given in the last treatment session in week 12, 16, 20 or 24 of PUVA therapy). Maintenance treatment will be given once a week for one month (4 weeks), every 2 weeks for 2 months (8 weeks) and after three months once a month over 6 months (Appendix: Figure 1). After 9 (10, 11, or 12) months of maintenance therapy (14 treatments) patients will discontinue therapy. If PUVA treatment does lead to erythema during maintenance therapy, the dose for the next treatment will be reduced by up to 30%.

Patients with recurrence during PUVA maintenance will discontinue the study. After the end of maintenance therapy the patients will be followed up every three months in the first year after treatment, every 6 months in the second year and once a year from year 3 to 5 or until recurrence of the disease.

Arm B: control arm – Patients will receive no therapy. Patients are followed up at the same intervals like patients in study arm A (Appendix: Table 4).

Observatory patient arm:

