9.2 Discontinuation of the study

The investigator may discontinue the study anytime in the interest of the probands if severe adverse events or other unforeseen problems occur.

Ethics Committees concerned and competent authorities should be informed about premature discontinuation and its reason within 15 days.

10. Monitoring

Monitoring will be performed according to the monitoring plan of this study. The investigator will cooperate with the monitor and provide unrestricted access to source data and all other study materials.

The investigator will keep detailed records in the patient charts on study visits, distribution of study drugs, test results, concomitant diseases, and adverse events. The monitor will regularly verify entries on the CRFs with source data and check compliance with the study protocol and continuous data entry. The monitor will handle all data confidentially to ensure integrity and privacy of the study participants.

11. Data protection

Recording and analysis of personal data within this clinical trial will be performed according to applicable data protection laws, provided the study participant has consented to this prior to enrolment. Informed consent will include information on data protection as follows:

1. Data collected within this clinical trial will be recorded on case report forms, handled in a strictly confidential way.
2. If necessary for evaluation of the clinical trial, authorized personnel of the sponsor, of competent authorities and/or Ethics Committees may confidentially review personal data of the study participants at the trial site.

3. The study participant will be informed that participation in the clinical trial may be terminated at any time without giving a reason and without any consecutive disadvantage. However, due to legal requirements, inspection of personal data by authorized persons may be continued in a confidential manner.

12. Clinical evaluation and laboratory tests

Patients with histopathologically documented MF and clinical stage IA to II B, who have given informed consent and are willing to participate in the study should undergo the following testing and investigation:

12.1. Before treatment start - Pretreatment evaluation (see also Appendix: Table 4: Summary of visits and assessments) (Within 28 days before treatment start):

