- Medical history and clinical examination (if clinically palpable lymph nodes: lymph nodes ultrasounds); in case of ultrasonic suspicion of disease-specific lymph node involvement a lymph node biopsy and/or excision will be done
- Determination of mSWAT
- Skin biopsies for diagnostic purposes and for determination of cytokine levels as well as T-cell receptor rearrangement (TCR-R)
 - All standard study biopsies should be taken from the site of the marker lesion (defined at baseline). Biopsies should only be taken from other parts of the body (outside the area of the marker lesion) if the response at that site is clinically ambiguous.
- Ophthalmologic examination
- Laboratory tests: Hematology (hemoglobin, WBC with differential and platelet counts), serum biochemistry: serum AST (SGOT), ALT (SGPT), alkaline phosphatase, urea, creatinine, and glucose
- Antinuclear antibodies (dsDNA, Ro/SSA, La/SSB)
- Blood draw for cytokine, TCR-R and FOXP3 mRNA analysis and Cell free DNA BCT for blood tumor cell analysis (see Appendix: Table 5)
- Pregnancy test (for women with childbearing potential) in blood or urine
- Photographic documentation
- DLQI (Dermatology Life Quality Index)
- HADS (Hospital Anxiety and Depression Scale)

12.2. During treatment and in the follow-up period:

Assessments will be done, as described in Appendix Table 4 at specific time points. A biopsy after the start of PUVA therapy (e.g. scheduled at week 6 with a gray period of 2 weeks) should be taken on a day of PUVA treatment before UVA exposure.

For control purposes blood samples from a maximum of 30 healthy control subjects and 30 samples of normal skin available from other studies will be analyzed, together with the samples of this study.

13. Statistics

Previous studies have shown that MF lesions reappear after a very variable time interval with median 9 to 15 months, depending on the study [WACKERNAGEL]. PUVA maintenance therapy intends to prolong this lesion-free interval and to reduce recurrence rate after discontinuation of the maintenance therapy.

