| Randomization ^g | | | | x ^g | x ^g | x ^g | x ^g | | | | | | |

| | | |
|---|--|---|
| ^a TCR-R: T-cell receptor rearrangement and FOXP3 mRNA | ^b To analyse on site if procedure is available | ^c DLQI: Dermatology Life Quality Index |
| ^d HADS: Hospital Anxiety and Depression Scale | ^e Photographic assessment: optional in case of recurrence | ^f Before treatment start (within 4 weeks) |
| ^g Randomization: time of randomization at V4a, V4b, V4c or V4d if complete remission | ^h For patients who were not randomized in Group A or B | ⁱ Pregnancy test: has to be taken once a month till Randomization and after Randomization in Study Arm A |
| ^j 3 weeks after treatment start | ^k 6 weeks after treatment start | ^l Time of visits: depends on the numbers of optional visits |
| ^m 12 weeks after start of maintenance therapy | ⁿ 24 weeks after start of maintenance therapy | ^o 36 weeks after start of maintenance therapy |
| ^p every three months in the first year, every 6 months in the second year and once a year in years 3 to 5 after PUVA maintenance therapy | ^q Skin biopsy: in the case of complete clinical response at the time of randomization | |

Table 5: Cytokines and chemokines will be analyzed, including:

IL-1a, IL-1b, IL-4, IL-6, IL-9, IL-10, IL-13, IL-12p35, IL-12p40, IL-12p70, IL-17A, IL-17F, IL-23, IL-23p19, TGF- β 1, IFN- γ , TNF- α , G-CSF, GM-CSF, MCP-1, RANTES, KC, IP-10, MIP-1a and others

Figure 1:

TRIAL DESIGN (STUDY M-PUVA 2012)

[figure not shown]

Figure 1: ↓ PUVA exposure: Month 1-3 (and optional Month 4-6): 2x/week, Month 4: 1x/week, month 5-6: 1x/2 weeks, month 7-12: 1x/month

Follow-up: year 1: 1 visit/3 months, year 2: 1 visit/6 months, year 3-5: 1 visit/year

Figure 2:

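### The 7-day pregnancy test in section 4.1 is timed to randomisation, 12 to 24 weeks after oral 8-MOP/UVA begins, and the test before the first dose may be 28 days old

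*Combined protocol and SAP*

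**What the plan says.** Section 4.1 (Inclusion Criteria) asks for a negative serum or urine β-HCG test "within seven (7) days prior to randomization". Section 4.2 excludes pregnant and lactating women but attaches no test date to that exclusion.

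Sections 5 and 13.3 put randomisation at week 12, 16, 20 or 24 of PUVA, after 24, 32, 40 or 48 treatments, and only for patients in complete remission. Table 4, footnote g, confirms this timing. Patients not in complete remission by week 24 "will discontinue active study participation and will enter an observatory study arm", so they are never randomised.

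The test that precedes treatment belongs to the pretreatment evaluation in section 12.1, headed "Within 28 days before treatment start". The entry reads "Pregnancy test (for women with childbearing potential) in blood or urine" and gives no tighter window. Table 4 repeats the 4-week window for visit 1 (footnote f). Its pregnancy-test row is labelled monthly and has further marks at week 3, week 6 and week 12. Footnote i asks for monthly tests until randomisation, and afterwards in Arm A.

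**The concern.** The shortest test window in the protocol is tied to an event that comes months after exposure has begun. A woman can meet every stated requirement and take her first oral 8-MOP dose on a negative test that is four weeks old.

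The protocol excludes pregnancy at entry (4.2) and lists it as a reason for drop-out (9.1). The exclusion can act only on what a test or the patient reveals. A pregnancy that becomes detectable between a test on day -28 and day -7 could go unnoticed at the first dose, whereas a test in the last 7 days would find it. A pregnancy too early for any test would be missed under either rule.

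At stake is participant safety during initial PUVA. The randomised comparison, the sample size and the analysis are not involved.

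**Working it through.** The plan gives no figure to reproduce. The check is a timeline, with day 0 as the first PUVA treatment.

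**Inputs**
- 7-day window before randomisation: section 4.1.
- Randomisation at week 12, 16, 20 or 24: sections 5 and 13.3.
- Two treatments per week in the initial phase: section 5.
- Pretreatment window of 28 days: section 12.1; 4 weeks in Table 4, footnote f.
- Monthly repeat tests: Table 4, footnote i.
- First on-treatment test mark at week 3: Table 4.

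**1. When the window in 4.1 opens**

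| Randomisation | Day | Window opens | Treatments by randomisation |
|---|---|---|---|
| Week 12 | 12 × 7 = 84 | 84 − 7 = 77 | 12 × 2 = 24 |
| Week 24 | 24 × 7 = 168 | 168 − 7 = 161 | 24 × 2 = 48 |

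For patients who are not randomised it never opens, although they may also receive up to 48 treatments.

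**2. Can the criterion work at entry as written?** The rest of section 4 is applied at entry. Another criterion in 4.1 concerns illness or infection "at time of entry into the study that could interfere with planned treatment". Section 4.2 excludes "PUVA (oral or topical) treatment within the last 3 months". Taking 3 months as about 13 weeks and assuming no skipped sessions, a patient at randomisation has had 24 treatments in that period (week 12) or 13 × 2 = 26 (weeks 16 to 24). Every randomised patient would meet that exclusion if it were applied then. Section 4 must therefore be applied before treatment starts, when the 7-day window before randomisation has not opened.

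**3. Oldest permitted test at the first dose**
- As written: 28 days.
- With a 7-day limit tied to first exposure: 7 days.
- Difference: 28 − 7 = 21 days. Ratio: 28 / 7 = 4.

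**4. Does monthly testing close the gap?** Take a screening test on day -28.
- Repeat a strict month later (28 to 31 days): −28 + 28 = day 0 to −28 + 31 = day +3. This can fall after the first dose.
- Repeat at the next visit marked in Table 4: week 3 = day 21, which is 28 + 21 = 49 days after the screening test and after about 3 × 2 = 6 treatments.

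On neither reading is a recent test guaranteed before the first dose.

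**The case against.** The strongest case against is that the protocol already has several safeguards: a pretreatment test, the exclusion in 4.2, monthly tests with marks at weeks 3 and 6, and a drop-out rule in 9.1 that names pregnancy. These apply to all women on initial PUVA, whether or not they are later randomised. The 77 to 161 days therefore describe the clause in 4.1 alone and are not an untested period. The gap is largest only when screening falls at the far edge of its window. On a strict monthly reading the repeat test comes by day +3, after one or two treatments.

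A test before randomisation also has a purpose, because randomisation decides who receives 14 further treatments. If the authors used the word randomisation loosely for enrolment, sites may already be testing at the right time. Finally, the documents state no fetal risk from 8-MOP/UVA: the side effects in section 8 include none, and the product information that section 5 refers to was not available for this review. Nothing in the protocol calls a 28-day test inadequate.

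Much of this stands, and it limits the weight of the point. The safeguards shorten an unnoticed exposure, and the number of women concerned is probably small. They do not place a recent test before the first dose. If the wording was loose, it contradicts sections 5 and 13.3 and Table 4, and the same sentence needs the same repair. The 7-day standard and the exclusion are the protocol's own, so the point needs no outside source on fetal risk.

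**Conclusion.** The concern holds. The test required before the first dose may be 28 days old, while the protocol's own 7-day limit applies only from day 77 to day 161 onward, and only to patients who are randomised. Tying the 7-day limit to first exposure would cut the oldest permitted test by 21 days, a factor of 4. It would not shorten the interval to the next monthly test.

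The documents do not allow the number of women, or of pregnancies found earlier, to be computed. The conclusion assumes that the removed consent pages contain no test tied to the first dose. It is a participant-safety correction that the sponsor should make, and it has no bearing on the primary endpoint.

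**What to change.** In section 4.1, require a negative serum or urine pregnancy test within 7 days before the first 8-MOP/UVA exposure. If 8-MOP is taken for the MPD phototest, that phototest should count as the first exposure: it is read at 72 hours, so it comes at least 3 days before the first treatment, or 6 if the second series is needed.

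Keep the test within 7 days before randomisation as a re-check before possible maintenance. Leave the monthly testing, and the 28-day window for all other pretreatment assessments, as they are.

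The cost is one sentence, and at most one extra urine strip (already allowed by Table 4) for a woman whose screening test is more than 7 days old at first exposure. Visits, doses, sample size and analysis do not change.

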- Stable disease (SD): less than 50 % reduction (from baseline) and less than 25 % increase of skin disease (compared with the smallest mSWAT since treatment started)
- Progressive disease (PD): more than 25 % increase in mSWAT compared with the smallest mSWAT since treatment started.

7. Definition of recurrence

Recurrence will be defined as re-occurrence of cutaneous disease, as determined by mSWAT at any time point (Complete remission = 100% clearing of skin disease (mSWAT of 0); recurrence is reappearance of skin lesions (mSWAT \geq 1)) [OLSEN (b)]: . If there is clinical doubt of continuous remission, a biopsy should be performed.

8. Adverse Events

Definitions

Adverse Event (AE)

Any untoward medical occurrence in a patient or clinical investigation subject administered a pharmaceutical product and which does not necessarily have a causal relationship with this treatment. An adverse event (AE) can therefore be any unfavourable and unintended sign (including an abnormal laboratory finding), symptom, or disease temporally associated with the use of a medicinal (investigational) product, whether or not related to the medicinal (investigational) product (see note for guidance on Clinical Safety Data Management: Definitions and Standards for Expedited Reporting).

Serious Adverse Event (SAE), Serious Adverse Drug Reaction (Serious ADR)

Any untoward medical occurrence that at any dose:

- results in death,
- is life-threatening,
- requires inpatient hospitalisation or prolongation of existing hospitalisation,
- results in persistent or significant disability/incapacity,

or

- is a congenital anomaly/birth defect

Suspected unexpected serious adverse drug reactions (SUSARs)

Suspected Unexpected Serious Adverse Drug Reactions (SUSARs) are side effects (probably or definitely connected with the administration of the investigational product), the nature or severity of which are inconsistent with the information available about the product. Information about the trial product contained in the SmPC (Summary of medicinal Product Characteristics) should be used to verify if the adverse reaction has been previously described.

Safety reporting

Investigator:

The investigator is responsible for reporting AEs, SAEs and SUSARs to the sponsor.

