All serious adverse events (SAEs) should be reported immediately to the sponsor except for those SAEs that the protocol or other document (e.g. Summary of Product Characteristics) identifies as not needing immediate reporting. The immediate reports should be followed promptly by detailed, written reports.

The immediate and follow-up reports should identify subjects by unique code numbers assigned to the trial subjects rather than by the subjects' names, personal identification numbers, and/or addresses. The investigator should also comply with the applicable regulatory requirement(s) related to the reporting of unexpected serious adverse drug reactions to the regulatory authority(ies) and the ethics committee.

Adverse events and/or laboratory abnormalities identified in the protocol as critical to safety evaluations should be reported to the sponsor according to the reporting requirements and within the time periods specified by the sponsor in the protocol.

For reported deaths, the investigator should supply the sponsor and the ethics committee with any additional requested information (e.g., autopsy reports and terminal medical reports).

Sponsor:

The sponsor should keep records of all AEs reported by the investigators. These records should be forwarded upon request to the competent authority of the region where the Clinical Trial is performed.

In case of death or immediate danger of life caused by a SUSAR the competent authorities and Ethics Committee(s) concerned should be informed by the sponsor within 7 days after the event becomes known to the sponsor. Additional information should be given within further 8 days.

All other SUSAR ("requires inpatient hospitalisation or prolongation of existing hospitalisation, results in persistent or significant disability/incapacity, or is a congenital anomaly/birth defect) should be reported as soon as possible, at latest within 15 days after the event becomes known to the sponsor, to the competent authorities and Ethics Committee(s) concerned.

Information on SUSARs should be forwarded to all other investigators of the same clinical trial by the sponsor. Once yearly during the trial, a safety report and a listing of all SUSARs that occurred during the trial should be forwarded to the competent authorities and to the Ethics Committees concerned by the sponsor.

Known Side effects of PUVA-Therapy

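### The SUSAR definition in section 8 requires a probable or definite link to the product, so an unexpected serious event judged only possibly related triggers none of the sponsor's SUSAR duties

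*Combined protocol and SAP*

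**What the plan says.** Section 8 defines three classes of event. The adverse event definition holds whether or not there is a causal link. Serious adverse events and serious adverse drug reactions share one definition, based on outcome alone. Causality enters only in the third class, the SUSARs, which "are side effects (probably or definitely connected with the administration of the investigational product), the nature or severity of which are inconsistent". The comparison is with existing product information, and the SmPC is the reference for what is already known.

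The sponsor's duties follow under Safety reporting in the same section:

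- Fatal or life-threatening cases: "In case of death or immediate danger of life caused by a SUSAR the competent authorities and Ethics Committee(s) concerned should be informed". The time limit set for this report is "within 7 days after the event becomes known to the sponsor".
- All other SUSARs go to the same bodies "at latest within 15 days after the event becomes known to the sponsor".
- Other sites: "Information on SUSARs should be forwarded to all other investigators of the same clinical trial by the sponsor".
- Once a year, "a safety report and a listing of all SUSARs that occurred during the trial should be forwarded" to the authorities and ethics committees.

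On the investigator's side, "All serious adverse events (SAEs) should be reported immediately to the sponsor except for those SAEs" that the protocol or another document exempts. A general clause adds: "The investigator should also comply with the applicable regulatory requirement(s) related to the reporting of unexpected serious adverse drug reactions".

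**The concern.** The name of the class and its content disagree. A reaction can be suspected before anyone would call it probable, yet the definition admits only the two upper grades. Because the sponsor's outward duties use the term SUSAR, the definition decides which events leave the sponsor on a fixed timetable and which are passed to the other investigators.

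What is at stake is participant safety, not the endpoint or its analysis. The protocol expects more than one site: it refers to other investigators, and Table 4 marks one assay as being for Graz only. If an unexpected serious event at one site is graded possible, nothing in the protocol text obliges the sponsor to tell the sites that are still treating patients.

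**Working it through.** The plan states no figure on this point and no arithmetic applies. The check is to trace one event through the text.

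**Step 1: find every causality threshold.** The SUSAR definition contains the only one in section 8. No causality scale appears in the protocol or its appendix tables, and no clause widens the definition to a possible link.

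**Step 2: classify a test event.** Take an event that is serious, not described in the SmPC, and judged possibly related.

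- Serious: yes.
- Nature or severity inconsistent with the product information: yes.
- Link probable or definite: no.

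The third condition fails, so the event is not a SUSAR.

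**Step 3: apply the four SUSAR duties to the same event under two gradings.**

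| Sponsor duty | Graded probable | Graded possible |
|---|---|---|
| 7-day report (fatal or life-threatening) or 15-day report (all others) | one of the two applies | neither applies |
| Information to all other investigators | applies | does not apply |
| Yearly SUSAR listing | applies | does not apply |

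**Step 4: look for another route for the event graded possible.**

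- *SAE report to the sponsor (section 8).* It does not depend on causality, so the sponsor generally learns of the event. The route ends at the sponsor and carries an exception.
- *Sponsor's records of all AEs (section 8).* They go to the competent authority only when it asks for them.
- *Yearly safety report (section 8).* It may mention the event, but its content is not defined, and it goes to authorities and ethics committees, not to investigators.
- *Investigator's regulatory compliance clause (section 8).* It reaches the authorities and the ethics committee and does not use the SUSAR term. It states no causality threshold and no deadline.
- *Reported deaths (section 8).* The investigator gives the sponsor and the ethics committee further information if they request it.
- *Drug Law clause (section 14).* It binds the trial as a whole. It too states no threshold and no deadline.

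Several of these routes lead beyond the sponsor. None restores the 7-day or 15-day limit in the protocol text, and none requires other sites to be informed.

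**The case against.** The strongest reply is that the trial is bound by regulatory requirements (section 8) and by the national Drug Law (section 14), so a careful sponsor may report more than the SUSAR paragraph demands. This stands in part. What the law requires is not in the documents, so the gap in practice cannot be established from them. But a general clause does not change the specific definition that staff will apply when they classify an event. If the two differ, the protocol should not leave them to discover it.

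A second reply is that the documents name no causality grades, so the category of possibly related is brought in from outside. That is true, but any judgement below probable is excluded in the same way, whatever it is called.

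A reader might also infer four stronger points, which the documents do not support:

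- *Such an event has no other route and gets no expedited report at all.* Step 4 shows other routes. The statement is true only of the sponsor's SUSAR duties.
- *A serious reaction put down to UVA falls outside the definition because it names only the product.* This is at most an ambiguity. Section 8.2 treats drug and light together, arm A is defined as the combination, and burns are listed there as known effects, so they are a poor example of an unexpected reaction.
- *Stopping the study under section 9.2 depends on the definition.* That section refers to severe adverse events and unforeseen problems and is not conditioned on SUSAR status.
- *First unexpected events are usually graded possible.* Nothing in the documents supports a statement about how often this happens.

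**Conclusion.** The point holds as a fault in a stated rule. The definition contradicts its own name. Followed as written, it leaves an unexpected serious event graded below probable outside the 7-day and 15-day reports, the information to other investigators and the yearly SUSAR listing. The clearest practical loss is the information to other sites, because no other clause provides it.

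The number of events affected cannot be given: the documents contain neither an expected SAE rate nor a split by causality grade. The conclusion rests on reading section 8 as written and on the assumption that staff classify events by its definition. It does not claim that such events go unreported. The change should be made, since the fault lies in a safety pathway and the remedy is small.

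**What to change.** In the SUSAR definition in section 8, replace the bracketed causality condition with wording such as: *judged at least possibly related to the study treatment (possible, probable or definite)*. Leave the condition on unexpectedness and the time limits as they are. Add to the safety reporting text that causality is recorded on that scale for each SAE. The grades are proposed here, because the protocol defines none; the essential step is to state which grades count as suspected.

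The cost is one reworded sentence in an amendment and one item to record per SAE. The downside is that a few more events may need expedited reporting. No dose, schedule, endpoint or analysis changes.
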